### 6 Study Assessments and Procedures

Study procedures and their timing are summarized in the SoA.

Adherence to the study design requirements, including those specified in the SoA, is essential and required for study conduct.

All screening evaluations must be completed and reviewed to confirm that potential participants meet all eligibility criteria. The Investigator will maintain a screening log to record details of all participants screened and to confirm eligibility or record reasons for screening failure, as applicable.

# 6.1 In-office study set-up

• Methods: Participants will be connected to the TheraPAP circuit through a CPAP mask (which will be the same that they will be given for their at-home treatment) and two 22 mm hoses to prevent cross contamination. A panoramic of the setup in the patient room is shown in Figure 1.

[figure not shown]

Figure 1. Continuous positive airway pressure (PAP)/TheraPAP circuit. TPAP, TheraPAP device.

# 6.2 Safety Assessments

Planned time points for all safety assessments are provided in the SoA. Safety assessments will include monitoring and recording of AEs, SAEs, and recording of study discontinuations.

# 6.3 Adverse Events and Serious Adverse Events

The definitions of AEs and SAEs can be found in Regulatory authorities of certain countries, IRBs, IECs, and/or the Sponsor's Clinical Quality Assurance Group (or designee) may wish to carry out source data checks and/or on-site audit inspections. Direct access to source data will be required for these inspections and audits; they will be carried out giving due consideration to

data protection and medical confidentiality. The Investigator assures the Sponsor and affiliates or designees (such as a CRO) of the necessary support at all times.

Appendix 3.

Adverse events will be reported by the participant.

The Investigator and any qualified designees are responsible for detecting, documenting, and reporting events that meet the definition of an AE or SAE and remain responsible for following up on AEs that are serious, considered related to the study device or the study, or that caused the participant to discontinue the study.

Appendix 3.

# 6.3.2 Method of Detecting AEs and SAEs

Care will be taken not to introduce bias when detecting AEs and/or SAEs. Open-ended and non-leading verbal questioning of the participant is the preferred method to inquire about AE occurrence.

# 6.3.3 Follow-up of AEs and SAEs

Ongoing AEs and SAEs will be followed until resolution or stability as determined by the Investigator.

# 6.3.4 Regulatory Reporting Requirements for SAEs

Prompt notification (within 24 hours, see Regulatory authorities of certain countries, IRBs, IECs, and/or the Sponsor's Clinical Quality Assurance Group (or designee) may wish to carry out source data checks and/or on-site audit inspections. Direct access to source data will be required for these inspections and audits; they will be carried out giving due consideration to data protection and medical confidentiality. The Investigator assures the Sponsor and affiliates or designees (such as a CRO) of the necessary support at all times.

Appendix 3) by the Investigator to the Sponsor of an SAE is essential so that legal obligations and ethical responsibilities towards the safety of participants and the safety of a study treatment under clinical investigation are met.

The Sponsor has a legal responsibility to notify both the local regulatory authority and other regulatory agencies about the safety of a study treatment under clinical investigation. The Sponsor will comply with country-specific regulatory requirements relating to safety reporting to the regulatory authority, IRB, and Investigators.

Investigator safety reports must be prepared for suspected unexpected serious adverse reactions (SUSAR) according to local regulatory requirements and Sponsor policy and forwarded to Investigators, as necessary.

# 7 Statistical Considerations

# 7.1 Sample Size Determination

A score of 1 and 2 will be combined for a preference of Pressure 1 and a score of 4 and 5 will be combined for a preference of Pressure 2. A score of 3 indicates no preference. In a 2x2 Williams

Cross over design with 2 treatments, where the endpoint is a proportion, (i.e., the proportion that prefer one pressure over another) the sample size per sequence that is needed to achieve 80% power, based on a two-sided 5% significance level, with a total of 6 comparisons results in a total number of participants of 384.

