### **Overall Design:**

The TheraPAP Comfort Study is an in-office study to assess comfort of TPAP vs. CPAP in CPAP-naïve patients with OSA during supine wakefulness. Patients will be recruited after routine outpatient visits. They will be asked to breath normally for approximately 1 minute in supine wakefulness while being administered 2 different pressure therapies for comparison. For TPAP therapies, each baseline pressure (9 or 13 cmH2O) will consider 3 separate settings, TPAP A,TPAP B and TPAP C for 9, then TPAP D,TPAP E and TPAP F for 13.

At the first baseline pressure, patients will be asked to choose their preference between CPAP and TPAP A. This will be the primary endpoint. If TPAP A is chosen, testing will move on to the second baseline pressure. If CPAP is preferred, CPAP will then be compared to TPAP B. If TPAP B is chosen, testing will move on to the second baseline pressure. If CPAP is again chosen as preferred, it will be lastly compared to TPAP C, the latter two comparisons being secondary endpoints.

<sup>1 TPAP will be used herein to refer to the actual modified PAP delivery.

At the second baseline pressure, patients will be asked to choose their preference between CPAP and TPAP D. This will be the primary endpoint. If TPAP D is chosen, testing will move on to the second baseline pressure. If CPAP is preferred, CPAP will then be compared to TPAP E. If TPAP E is chosen, testing will move on to the second baseline pressure. If CPAP is again chosen as preferred, it will be lastly compared to TPAP F, the latter two comparisons being secondary endpoints.

Baseline CPAP (cmH2O)	TPAP Setting	Pressure Drop 1 (cmH 2 O)	Pressure Drop 2 (cmH 2 O)
	TPAP A	2	2
9	TPAP B	1	2
	TPAP C	1	1
	TPAP D	2	3
13	TPAP E	2	2
	TPAP F	1	2

**Table 1**. Pressure Drops 1 and 2 refer to the first and the second drops in pressure that occur during inspiration and are maintained until about halfway through expiration. The overall pressure drops consist of Drop 1+ Drop 2. CPAP, continuous positive airway pressure.

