# 4.2.2 In-office study

Individuals who agree to participate will be asked to sign an informed consent prior to commencement of study procedures upon their arrival at the clinic.

The following activities will also occur:

- Height and weight will be measured.
- Randomization of CPAP/TPAP order.

To begin the study, each participant will lay in a supine position on a reclining chair in the office and all therapy comparisons will be made in this orientation. Subsequently, each patient will be studied on two different baseline positive pressures: 9 and 13 cmH2O. At either of the above pressures, each patient will assess CPAP against 2 different pressure drops in one-to-one comparisons.

For the baseline CPAP of 9 cmH2O, TPAP will be set to:

- TPAP A
- Followed by TPAP B if CPAP was previously preferred
- Followed by TPAP C if CPAP was previously preferred

For the baseline CPAP of 13 cmH2O, TPAP will be set to:

- TPAP D
- Followed by TPAP E if CPAP was previously preferred
- Followed by TPAP F if CPAP was previously preferred

Note that TPAP drops, designated as x/y, indicate first and second drop of PAP, starting during inspiration.

Assessment of comfort will be made by comparing one-to-one TPAP against each other or against CPAP by having the patient breathe on the pressure for one minute (or more as needed based on the judgment of the Study Coordinator) and then indicating which is more comfortable

by voice or hand sign. The indicated choice will be recorded by the Study Coordinator. The patient will be able to ask to repeat settings as often as needed to make the most informed choice.

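### Section 7.1 attaches 80% power at N = 384 to six comparisons, but four of them are run only in participants who have already chosen CPAP, so 80% is not secured for those four

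*Combined protocol and SAP*

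**What the plan says.** Section 7.1 (Sample Size Determination) gives one calculation for a two-treatment crossover with a proportion as endpoint: "80% power, based on a two-sided 5% significance level, with a total of 6 comparisons results in a total number of participants of 384". It gives no assumed preference, no null value and no account of how the six comparisons enter the number. It does not limit the 80% to the primary endpoints.

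There are six CPAP-versus-TPAP comparisons: A, B and C at 9 cmH2O, and D, E and F at 13 cmH2O. The synopsis (Overall Design) makes A and D primary and runs the others conditionally. At the first pressure, testing stops once TPAP is chosen, and for the last step: "If CPAP is again chosen as preferred, it will be lastly compared to TPAP C, the latter two comparisons being secondary endpoints". At the second pressure: "If CPAP is preferred, CPAP will then be compared to TPAP E". Section 4.2.2 repeats the conditions: "Followed by TPAP B if CPAP was previously preferred" and "Followed by TPAP F if CPAP was previously preferred".

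One sentence in 4.2.2 does not fit this sequence: at each pressure "each patient will assess CPAP against 2 different pressure drops in one-to-one comparisons". Under the conditional steps a participant makes one, two or three comparisons per pressure. The working below follows the conditional steps, which both the synopsis and 4.2.2 set out.

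**The concern.** A single N with a single power for six comparisons reads as if all six have that power. Four of the six have denominators that depend on earlier answers and fall below 384 as soon as anyone chooses TPAP. The better TPAP does at the first step, the fewer participants are left for the later ones.

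Two things are at stake. First, a null result on B, C, E or F could be taken as a negative from an 80%-powered comparison when only a small part of the 384 was tested. Second, because 7.1 names no effect, a reader cannot tell which preference 384 was meant to detect even for A and D.

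**Working it through.** **Inputs from the protocol.** N = 384, 80% power, two-sided 5%, six comparisons (7.1); conditional sequence (synopsis, Overall Design; 4.2.2).

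**Assumptions, because the protocol gives none.** One-sample test of the preference proportion against 50%, normal approximation, no ties, sample sizes set at their expected values. With true TPAP preference p and two-sided critical value z:

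power(n, p) = Φ( [ (p − 0.5)√n − 0.5z ] / √(p(1 − p)) ), mirrored for p below 0.5.

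**Step 1: can 384 be reproduced?** Not as a power calculation, since no effect is stated. Several constructions fit the number:

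- 384 as the number each comparison needs. Solving for 80% power gives p = 57.1% (alpha 0.05), 57.8% (0.05/2) or 58.8% (0.05/6).
- 384 = 6 × 64. At n = 64, 80% power needs p = 67.2% (alpha 0.05).
- A precision formula, 1.96² × 0.25 / 0.05² ≈ 384, which is not a power calculation.

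The protocol does not say which of these, if any, was used.

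**Step 2: numbers reaching each comparison.** If a share q chooses CPAP at each step:

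- A, D: 384
- B, E: 384q
- C, F: 384q²

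**Step 3: equal preference at every step (q = 1 − p), 384 taken as each comparison's requirement.** Alpha 0.05, p = 0.5713, √(p(1 − p)) = 0.495:

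- A/D: (0.0713 × 19.60 − 0.98) / 0.495 = 0.84, power 80%
- B/E: n = 384 × 0.4287 = 164.6; (0.0713 × 12.83 − 0.98) / 0.495 = −0.13, power 45%
- C/F: n = 384 × 0.4287² = 70.6; (0.0713 × 8.40 − 0.98) / 0.495 = −0.77, power 22%

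| Two-sided alpha | p giving A/D 80% | B/E: n, power | C/F: n, power |
|---|---|---|---|
| 0.05 | 57.1% | 165, 45% | 71, 22% |
| 0.05/2 | 57.8% | 162, 40% | 68, 17% |
| 0.05/6 | 58.8% | 158, 34% | 65, 11% |

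Under this construction the shortfall appears for each way of reading alpha.

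**Step 4: larger effects, same assumption, alpha 0.05.** B/E reach 80% from p of about 61.4% (n about 148). C/F do not reach 80% at any p between 50% and 95%: the highest power is 71.5%, at p of about 76% with n about 22. A normal approximation is rough at that size; an exact binomial test averaged over the random n gives about 63%.

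**Step 5: the 6 × 64 construction.** At p = 67.2%, B/E have 384 × 0.328 ≈ 126 participants and about 98% power, which is adequate. C/F have 384 × 0.328² ≈ 41 and 60.5%.

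**Step 6: equal preference dropped, alpha 0.05.**

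| q | n for B/E | Preference needed for 80% | n for C/F | Preference needed for 80% |
|---|---|---|---|---|
| 0.5 | 192 | 60.0% | 96 | 64.1% |
| 0.3 | about 115 | 62.9% | about 35 | 73.0% |

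**Step 7: CPAP preferred (equal preference, p below 50%, alpha 0.05).** More participants then reach the later steps. The two-sided test has 80% power for B/E at p of about 40.8% or lower (n about 227) and for C/F at about 38.5% or lower (n about 145).

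**The case against.** The strongest reply is that 7.1 does not say each of the six comparisons has 80% power. The six may be an alpha adjustment protecting A and D, or a multiplier, and power statements usually refer to primary endpoints. Sections 7.1 to 7.4 describe no test of B, C, E or F, so the misread null result is a possible misreading rather than a planned inference. This stands as a limit on the claim: what can be said is that 80% is not secured for the four, not that they are known to be underpowered. It does not rescue the sentence, which names six comparisons when only two are primary.

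The illustration also leans on equal preference at each step. Participants reaching B, C, E and F are selected for having chosen CPAP and then face different pressure drops, so their preference could differ in either direction. If half choose CPAP at each step and 65% of those then tested prefer TPAP, B/E have about 99% power and C/F about 85%. And if 384 means 6 × 64, B/E are adequate. Both points stand: the low percentages are scenario values, not the trial's power.

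Finally, the one-sample normal approximation is a reviewer's choice; 7.1 refers to a 2x2 Williams crossover sized per sequence. A different test would move the figures. It would not restore the participants who leave the sequence on choosing TPAP.

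**Conclusion.** The concern holds. The 80% attached to six comparisons is not secured for the four conditional ones, because their denominators shrink with every TPAP choice and 7.1 makes no allowance for this. That conclusion follows from the design and needs no assumed effect.

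The size of the loss does depend on assumptions. With equal preference above 50%, and 384 taken as each comparison's requirement, B/E have 34% to 45% power and C/F 11% to 22% at the preference where A and D have 80%, depending on alpha. With larger preferences, a different construction of 384, or a marked preference for CPAP, some or all of the four can be adequately powered.

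All four are secondary endpoints, and the conditional testing leaves the planned number for A and D intact. The point should be fixed, but it does not threaten the primary comparisons. The missing planning preference does affect A and D, since their 80% cannot be tied to any stated effect.

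**What to change.** In section 7.1:

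1. Limit the 80% power statement to CPAP versus TPAP A at 9 cmH2O and CPAP versus TPAP D at 13 cmH2O, the only comparisons planned in all participants.
2. State the assumed preference and how the six comparisons and alpha produce 384. If there was no planned effect, say so and give the detectable preference at N = 384 for the alpha actually used: 57.1% (0.05), 57.8% (0.05/2) or 58.8% (0.05/6), on the one-sample test without ties.
3. State that B, C, E and F have smaller, outcome-dependent denominators (384q and 384q² if a share q chooses CPAP at each step) and no secured power. Report them as estimates with 95% confidence intervals and actual denominators, described as results among participants who had already chosen CPAP once or twice.
4. Before adding any allowance for ties, reconcile the outcome scale. Section 7.1 uses a 1 to 5 score in which "A score of 3 indicates no preference", while 4.2.2 has the participant breathe on the pressure "and then indicating which is more comfortable".
5. Reconcile the 4.2.2 sentence on two pressure drops per participant with the conditional sequence.

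The cost is wording only, with no extra participants. The stated power becomes less favourable for the four secondary comparisons, and the sponsor must disclose its planning assumption or say that there was none.

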# 7.2 Randomization

All comparisons for each baseline pressure level (9 and 13 cmH2O) will be randomized separately for either baseline pressure per patient by using CPAP first in one case then CPAP second in the other. However, the baseline pressure order will not be randomized so that PAP-naïve patients can acclimate to PAP first at the lower pressure.

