# 4 Study Design

# 4.1 Overall Design

The TheraPAP Comfort Study is an in-office study to assess patient-level comfort on TPAP vs. CPAP. Pre-screening is conducted to establish potential eligibility with a previous sleep study showing an AHI>10 events/hr. Eligible participants will undergo an in-office study in which they will breathe in the supine position during wakefulness on CPAP and on TPAP. In cases where CPAP is preferred, TPAP will be dropped to different levels based on the baseline CPAP levels, according to Table 1. CPAP and TPAP will be administered in one and in the opposite order per patient following a randomized design, to simulate patient blinding to treatment.

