# 5.5 Measures to Minimize Bias

The order of CPAP tested first or second for each of the comparative tests for each baseline pressure will be randomized per patient, although the order of baseline pressure will be maintained for each patient starting with 9 cmH2O, then moving to 13 cmH2O.

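### The unit of order randomisation is undefined (Sections 5.5 and 7.2 differ); if one order is held within a pressure, a position effect biases secondary comparisons B, C, E and F against TPAP

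*Combined protocol and SAP*

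**What the plan says.** Four places describe the order of CPAP and TPAP:

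- Section 4.1: "CPAP and TPAP will be administered in one and in the opposite order per patient following a randomized design". The stated purpose is to simulate blinding of the patient.
- Section 4.2.2 has only a bullet: "Randomization of CPAP/TPAP order".
- Section 5.5: "The order of CPAP tested first or second for each of the comparative tests for each baseline pressure will be randomized per patient".
- Section 7.2: the order of the comparisons is drawn for each patient separately at the two pressures, "by using CPAP first in one case then CPAP second in the other". The word case is not defined.

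Sections 5.5 and 7.2 agree that 9 cmH2O always comes before 13 cmH2O.

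The later comparisons are gated. The synopsis (Overall Design) says of 9 cmH2O: "If CPAP is preferred, CPAP will then be compared to TPAP B"; C follows only if CPAP wins again. At 13 cmH2O, "If CPAP is preferred, CPAP will then be compared to TPAP E", and F follows in the same way. Section 3 makes A and D primary and B, C, E and F secondary.

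Section 7.1 sizes the trial as a 2x2 "Cross over design with 2 treatments, where the endpoint is a proportion", at a two-sided 5% level, with six comparisons and 384 participants. Section 4.2.2 lets participants repeat settings on request. No analysis is described that adjusts for order or for the gating.

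**The concern.** A randomisation list cannot be built from this text without choosing an interpretation. A draw for each comparison (5.5) and a draw for each pressure (7.2) are different designs, and the gating makes the difference count.

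Suppose one order is held for A, B and C. A participant inclined to pick, say, the second pressure felt is more likely to choose CPAP at A, and so to reach B, when CPAP was second. At B that participant meets CPAP second again. A position habit is then recorded as a repeated preference for CPAP. The same applies to E and F after D. Four of the six listed endpoints are exposed, and the trial could report that CPAP is preferred to the milder TPAP settings when participants have no preference.

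**Working it through.** **Plan's own figure.** The documents give no position effect, so there is no bias figure to reproduce. The 384 cannot be reproduced either, because Section 7.1 states no expected preference share. It is used here only as a head count.

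**Assumptions.** No true preference; orders allocated 1:1; every comparison ends in a choice; each share tested against 50% with an exact two-sided 5% binomial test. The test is this review's choice, as the plan names none. About 384 × 1/2 = 192 participants then reach B.

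**1. Common position effect, order held, choices independent.** Let P(choose the favoured slot) = 0.5 + d. Among those reaching B, a fraction 0.5 + d had CPAP in the favoured slot.

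- TPAP share at B = (0.5 + d)(0.5 − d) + (0.5 − d)(0.5 + d) = 0.5 − 2d².
- TPAP share at C = [(0.5 + d)²(0.5 − d) + (0.5 − d)²(0.5 + d)] / [(0.5 + d)² + (0.5 − d)²].

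| d | B | C | False rejection at B | at C |
|---|---|---|---|---|
| 0.10 | 0.48 | (0.36 × 0.4 + 0.16 × 0.6)/0.52 = 0.462 | about 7–8% | about 9–11% |
| 0.20 | 0.42 | (0.49 × 0.3 + 0.09 × 0.7)/0.58 = 0.362 | about 55–58% | about 80–81% |

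The ranges reflect whether the number reaching the comparison is fixed at its expected value or allowed to vary, and simulation error. With d = 0, the exact test at n = 192 rejects in 3.6% of trials.

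**2. Stable individual habits, order held.** A share s always picks the same slot; the rest choose 50/50.

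- Reach B: s/2 + (1 − s)/2 = 1/2. TPAP share at B = [(1 − s)/4] / (1/2) = (1 − s)/2.
- Reach C: s/2 + (1 − s)/4 = (1 + s)/4. TPAP share at C = [(1 − s)/8] / [(1 + s)/4] = (1 − s)/[2(1 + s)].

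| s | B | C | False rejection at B |
|---|---|---|---|
| 5% | 47.5% | 45% | about 10% |
| 10% | 45% | 41% | about 26% |
| 20% | 40% | 33% | about 77% |

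**3. A true preference for TPAP.** Take a true share of 0.6 and d = 0.10. TPAP is chosen with probability 0.5 when CPAP is in the favoured slot and 0.7 when it is not. Those reaching B split 0.5 : 0.3, that is 0.625 and 0.375. The share at B is 0.625 × 0.5 + 0.375 × 0.7 = 0.575. At d = 0.20 it is 0.75 × 0.4 + 0.25 × 0.8 = 0.50.

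**4. Order alternating between successive comparisons.** The sign at B reverses: (0.5 + d)² + (0.5 − d)² = 0.5 + 2d², or 0.52 at d = 0.10 and 0.58 at d = 0.20.

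**5. Stratifying by order.** In model 1 with d = 0.10, the TPAP shares at B are 40% in one order and 60% in the other. Their mean is 50%, so the bias goes. In model 2 with s = 20% and everyone's habit on the same slot, they are 0.20/0.60 = 33.3% and 50%, mean 41.7%. If habits split evenly between slots, both are 40%. The bias stays.

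**6. A fresh order for each comparison.** The order at B no longer depends on the choice at A, and the null share returns to 50% in both models. Selection remains. If individual preferences are stable and follow a Beta(a, a) distribution (assumed), the TPAP share at B among those who chose CPAP at A is a/(2a + 1): 5/11 = 45% for a = 5 and 2/5 = 40% for a = 2, with no order effect at all.

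**The case against.** A reader might infer that the plan states three incompatible rules. It does not. Section 4.1 fits 7.2 (one order at one pressure, the opposite at the other), and 5.5 can be read loosely in the same way. On its natural reading, 5.5 is already close to the remedy. What stands is two differing natural readings and an undefined unit.

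Section 7.2 never says outright that the order is held over A, B and C. If case means successive comparisons, the bias at B runs the other way, and under 5.5 there is none. That is correct, and it means the direction of error depends on how staff read the text.

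A reader might also take the bias as established. It needs a position effect, which the documents do not quantify. It is zero without one and only 2 percentage points at B when d = 0.10. The largest rejection rates need 20% of participants to ignore what they feel, and repeats on request may dilute any habit. The calculations leave out the no-preference score in Section 7.1, and a multiplicity adjustment would lower the rates: at 0.05/6, false rejection at B for s = 5%, 10% and 20% is about 2%, 10% and 54%. All of this limits the size but does not remove the mechanism.

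Finally, the primaries are untouched, and with order held the bias runs against the sponsor's own device. Both points are fair. They limit the consequence to four secondary endpoints.

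**Conclusion.** The point holds as a conditional one. Sections 5.5 and 7.2 describe different order schemes on their natural readings, and the unit of randomisation is undefined. If one order is held within a pressure, any position effect biases B, C, E and F against TPAP; if the order alternates, the bias at B favours TPAP. Over the assumed range, the null TPAP share at B runs from 48% (60% favour one slot, independent choices) to 40% (20% always pick the same slot), and at C from 46% to 33%.

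The documents do not support extending this to A and D: neither is gated on an earlier choice at its own pressure. Nor do they support the inference that order stratification is useless, since it removes the bias at B under a common position effect and fails only with stable individual habits. Nor does fresh randomisation make B, C, E and F population preference shares, because they still describe only people who have just chosen CPAP.

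This should be corrected before the randomisation list is made. An order that was not drawn independently, or not recorded, cannot be recovered afterwards.

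**What to change.** - State one rule, identically, in Sections 4.1, 4.2.2, 5.5 and 7.2: the CPAP/TPAP order is drawn 1:1, independently, for every comparison actually performed (A to F). The order at 13 cmH2O is then not tied to the order at 9 cmH2O.
- Keep the fixed sequence of 9 then 13 cmH2O.
- Record the order used at each comparison and report each preference share by order.
- Report B, C, E and F as conditional on CPAP having been preferred in the preceding comparison or comparisons at that pressure.

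Cost: up to six order entries per participant on the randomisation list, and aligned wording in four sections. No extra patients, staff or visit time.
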